***Sample size and power calculations:***

For purposes of sample size calculations we have simplified the analysis to focus on the difference in the E/e' ratio between the 2 intervention groups. Assuming a mean  $\pm$  standard deviation E/e' ratio  $15.2 \pm 6.4$  and 40% reduction in the LLTS group, 26 patients would provide greater than 80% power to detect the specified effect sizes at a two-sided  $\alpha$  level of 0.05.

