#### **Abstract:**

Heart failure with preserved ejection fraction (HFpEF) has become a major public health concern. Epidemiological studies have shown that the prevalence and hospitalizations related to HFpEF are increasing, and the growing elderly population is expected to further worsen these trends. Outcomes of patients with HFpEF are poor, and so far, no treatment has been shown to decrease morbidity or mortality. HFpEF is associated with various cardiovascular risk factors, including hypertension, atrial fibrillation and aging. The net result is impaired diastolic relaxation and filling of the left ventricle (LV), increased myocardial stiffness, impaired vascular compliance, and increased diastolic pressure. Recent animal and human studies support the notion that proinflammatory stimuli play a central role in the development of HFpEF. Specifically, comorbid conditions such as diabetes, obesity, hypertension and aging induce a systemic proinflammatory state, which in turn leads to decreased nitric oxide (NO) bioavailability, left ventricular fibrosis, increased myocardial stiffness, diastolic dysfunction and heart failure. Therefore, attenuating the proinflammatory state is an attractive therapeutic target for HFpEF.

The anti-inflammatory properties of the vagus nerve have been well established. In a recent proof-of-concept study in humans, we showed that in patients with drug-refractory atrial fibrillation, low-level transcutaneous vagus nerve stimulation (LLTS), delivered at the tragus of the ear for just one hour, significantly suppressed atrial fibrillation and decreased inflammatory cytokines. These results support the use of LLTS as a novel non-pharmacological treatment modality for atrial fibrillation and possibly other conditions, where inflammation plays a key role, including HFpEF. In this proposal, we hypothesize that short-term LLTS may reverse diastolic dysfunction in a 2x2 cross over study in patients with diastolic dysfunction. These proof-of-concept investigations will establish the first evidence of the effects of LLTS on LV diastolic dysfunction in humans and may provide the basis for the design of further human studies using this modality to target selected populations with HFpEF. In light of the increasing number of patients with HFpEF and the poor success of the currently available treatment options, an alternative approach such as the one tested in this grant proposal may benefit a large number of patients in Oklahoma.

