### **C. Preliminary studies**

#### ***Neuromodulation suppresses AF and inflammation in humans:***

We have recently shown that transcutaneous electrical stimulation of the auricular branch of the vagus nerve at the tragus (low-level tragus stimulation; LLTS) in humans has antiarrhythmic and anti-inflammatory effects. Forty patients with paroxysmal AF who presented in sinus rhythm for AF ablation, were randomized to either 1 hour of LLTS (n=20) or control (n=20). LLTS in the right ear, 50% lower than the voltage that slowed the sinus rate, was accomplished by attaching a flat metal clip onto the tragus. Under general anesthesia, AF was induced at baseline and after 1 hour of LLTS or sham stimulation and were analyzed for inflammatory cytokines, including TNF $\alpha$  and CRP, using a multiplex immunoassay. Pacing-induced AF duration decreased significantly by  $6.3 \pm 1.9$  min compared to baseline in the LLTS group, but not in the control ( $p=0.002$  for comparison between groups; Figure 2A). AF cycle length increased significantly from baseline by  $28.8 \pm 6.5$ ms in the LLTS group, but not in the control ( $p=0.0002$  for comparison between groups). Systemic (femoral vein) but not coronary sinus TNF $\alpha$  and CRP levels decreased significantly only in the LLTS group (Figure 2B). Importantly, the magnitude of decrease in TNF- $\alpha$  levels by LLTS was comparable with the difference between patients with active vs. inactive inflammatory diseases. We concluded that LLTS acutely suppresses AF and decreases inflammatory cytokines in patients with paroxysmal AF, supporting the emerging paradigm of neuromodulation to treat AF.

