## **D. Research Design and Methods**

### ***Specific Aim 1:***

To examine the effect of short-term LLTS on echocardiographic markers of diastolic dysfunction in patients with diastolic dysfunction. This is a prospective, randomized, 2x2 cross over pilot study. Patients who have been diagnosed with diastolic dysfunction by echocardiogram within 36 months of study enrollment will be eligible for enrollment in the study. Patients will be excluded if they have any of the following: left ventricular dysfunction (left ventricular ejection fraction <40%), significant valvular disorder (i.e., prosthetic valve or hemodynamically significant valvular diseases), recent (<6 months) stroke or myocardial infarction, severe heart failure (class III or IV), recurrent vasovagal syncope, unilateral or bilateral vagotomy, pregnancy or nursing and sick sinus syndrome (without a pacemaker), 2nd or 3rd degree AV block, bifascicular block or prolonged (PR>300ms) 1st degree AV block. Patients will be recruited from the outpatient clinics of OUHSC. All patients will receive 2 separate, 1-hour sessions, at least 1 day apart, of active and sham LLTS, with the sequence of the sessions being randomized. Patients will be randomly assigned (1:1) to active/sham or sham/active LLTS. LLTS will be performed using a transcutaneous electrical nerve stimulation (TENS) device with electrodes attached to the tragus of the ear, which is innervated by auricular branch of the VN. The SaluSTIM Digital TENS Unit distributed within the US by US Medical Inc will be used for LLTS or sham stimulation. The device will be connected to a clip electrode that will be attached to the external ear. In the active group, the ear clip electrode will be attached to tragus in the active stimulation group (Figure 3). This device was deemed as non-significant risk by the FDA (see attached letter). The same TENS protocol will be followed in sham LLTS arm, but the electrode will be placed on the ear lobe, which is devoid of vagus innervation. The TENS unit will be set at a pulse width of 100  $\mu$ s and a pulse frequency of 20 Hz. Amplitude will be titrated to the level of sensory threshold, typically in the range of 10–50 mA. In patients with pacemakers, the pacemaker will be tested with the TENS unit to assess for interaction. In case of interaction (the stimulation artifact of the TENS unit picked up by the pacemaker), the patients will be excluded from the study. Echocardiography will be performed after 30 minutes of LLTS or sham stimulation to assess diastolic function (Acuson SC2000, Siemens). Two-dimensional long axis and short axis LV images will be obtained and Pulse-wave Doppler spectra of mitral inflow (E and A waves), as well as mitral annulus tissue Doppler spectra will be recorded. The early diastolic mitral annulus velocity ( $e'$ ) will be used to assess diastolic function as previously described. The ratio of early to late mitral inflow Doppler velocity (E/A ratio) is a marker of LV diastolic relaxation and stiffness, and the E/ $e'$  ratio correlates well with LV filling pressures. In addition, LV diastolic strain, a sensitive marker of diastolic LV function, which independently predicts outcomes in patients with HFpEF, will be obtained off-line using a speckle-tracking algorithm (Acuson SC2000 eSie VVITM).

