**E. Statistical methods**

Continuous variables will be compared between the groups using repeated measures analysis of variance (ANOVA). Significant interactions will be followed by time trend analyses stratified by intervention group. For all pair-wise testing, we will adjust for multiple comparisons using Tukey's method. Statistical significance will be declared at  $p < 0.05$ .

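### Do the two-group wording and the atrial fibrillation citation behind the 40% E/e' reduction undermine the power claim for 26 patients?

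*Combined protocol and SAP*

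**What the plan says.** Under Sample size and power calculations, the plan simplifies the problem to the difference in the E/e' "ratio between the 2 intervention groups". It assumes a mean ± SD of 15.2 ± 6.4 (reference 41) and a "40% reduction in the LLTS group" (reference 31), and concludes that "26 patients would provide greater than 80% power to detect the specified effect sizes" at two-sided 0.05. It names no test, within-patient SD or correlation between sessions.

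The design is set out under Specific Aim 1 in section D. It is a 2x2 crossover with sequence randomized 1:1: "All patients will receive 2 separate, 1-hour sessions, at least 1 day apart, of active and sham LLTS". On imaging: "Echocardiography will be performed after 30 minutes of LLTS or sham stimulation to assess diastolic function". No scan before stimulation is listed.

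Reference 31 is the trial summarized in section C: "Forty patients with paroxysmal AF who presented in sinus rhythm for AF ablation, were randomized" to stimulation or control. The results given there are AF duration, AF cycle length, TNF-alpha and CRP. The Abstract says of the present study: "These proof-of-concept investigations will establish the first evidence of the effects of LLTS on LV diastolic dysfunction in humans".

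Section E plans repeated measures ANOVA and sets a threshold: "Statistical significance will be declared at" p < 0.05.

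**The concern.** Three features of the paragraph invite doubt.

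- **The effect size.** The 40% carries a citation to a trial in another disease, from which the protocol reports no diastolic measure. A reader could take it for an observed E/e' effect.
- **The comparison.** Wording about two intervention groups, next to a total of 26, suggests 13 against 13. On that reading the power claim appears to fail.
- **The reference point.** The paragraph does not say what the reduction is measured against.

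This paragraph is the only numerical basis for 26 patients. If it described the wrong design, the trial could be too small for its own target. If the 40% is optimistic, a non-significant result could be misread as absence of effect, because section E mentions only a p-value threshold.

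**Working it through.** **Inputs.** From Sample size and power calculations: mean 15.2, SD 6.4, reduction 40%, n = 26, two-sided alpha 0.05. The within-patient correlation rho is not given, so a range is used. The same SD of 6.4 is assumed in both sessions.

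**Target difference.** 0.40 × 15.2 = 6.08 units; 6.08 / 6.4 = 0.95 SD.

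**The plan's figure, for the planned crossover.** SD of the within-patient difference = 6.4 × √(2(1 − rho)). Noncentrality = 6.08 / (SD of difference / √26). Power comes from the noncentral t distribution with 26 − 2 = 24 df.

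| rho | SD of difference | Power, n = 26 |
|---|---|---|
| −0.3 | 10.32 | 82% |
| 0 | 9.05 | 91% |
| 0.3 | 7.57 | 97.5% |
| 0.5 | 6.40 | 99.6% |

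The stated figure is reproduced, with room to spare for any non-negative correlation. With only 20 completers at rho = 0, power is still 81%.

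**The literal two-group reading.** Standard error = 6.4 × √(2/13) = 2.51; noncentrality = 6.08 / 2.51 = 2.42; 24 df. Power is 64% (68% by the normal approximation), and 80% would need 19 per group.

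This figure depends on a common SD. If the SD fell in proportion to the mean, the active SD would be 0.6 × 6.4 = 3.84 and the pooled SD √((6.4² + 3.84²)/2) = 5.28. Two groups of 13 would then give about 80%. The documents state neither assumption for the active condition.

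**Which reading applies.** Every description of the design is of a crossover, and each patient has both sessions. Specific Aim 1 itself speaks of an active group and a sham arm within that crossover, so *group* is used there for the condition being delivered. The planned repeated measures ANOVA also fits within-patient data. With one scan scheduled per session and none beforehand, the only contrast the schedule supports is active against sham at 30 minutes, so the reference point of the reduction can be inferred.

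**Dependence on the 40%.** Crossover power with 26 completers:

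| True reduction | Units | rho = 0 | rho = 0.5 |
|---|---|---|---|
| 20% | 3.04 | 38% | 64% |
| 30% | 4.56 | 69% | 94% |
| 40% | 6.08 | 91% | 99.6% |

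**Precision.** The 95% CI half-width is t(0.975; 24 df) × SD of difference / √26: 3.7 units at rho = 0 and 2.6 at rho = 0.5. Such an interval tests 6.08 units. It tests a 40% reduction only if the sham mean is 15.2: with a sham mean of 12, 40% is 4.8 units; with 10, it is 4.0.

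**The case for a change.** The best case for a change is that it would be cheap and would make the claim checkable. The paragraph could call the 40% an assumption without direct E/e' evidence, name the comparison as active versus sham within patients, and commit to reporting the mean difference with its 95% CI and the SD of within-patient differences. The study is meant to inform later trials, and those quantities are what a later trial would need. The loose use of *group* also recurs in section E, so it is not an isolated slip.

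Part of this stands. The protocol does not explain how reference 31 leads to 40%, the phrase about groups is imprecise, and power falls quickly if the true effect is well below 40%.

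The rest does not carry a change. The sentence already introduces the 40% as assumed, and the Abstract's claim to be the first human evidence rules out reading it as an observed E/e' effect. Whether reference 31 supports 40% by analogy with another outcome cannot be judged from these documents. Section E sets a threshold but does not say that estimates or intervals will be withheld. An analyst reporting a crossover would give the mean difference, its interval and the SD as a matter of course.

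**Conclusion.** The concern does not call for a change. For the 2x2 crossover that the protocol plans, 26 completers give 91% power for 6.08 units at correlation 0 and SD 6.4 in both sessions, and more with positive correlation. The claim of more than 80% is therefore correct. The 64% belongs to a parallel-group trial that is not being run, and it also requires a common SD.

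The remaining points are a loose phrase for the active–sham contrast and a citation whose link to the 40% is not explained. Clarifying them would alter neither enrolment, design, test and alpha nor the conclusion. An effect smaller than assumed would lower power, but that is a risk of any first study of an outcome, and rewording the paragraph would not reduce it. This assessment rests on the plan's own mean and SD. Their source is titled as a study of heart failure with preserved ejection fraction, whereas eligibility requires only echocardiographic diastolic dysfunction, so how well they apply here is unknown.

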**F. Gender/Minority/Pediatric Inclusion for Research**

Participants will be age 18 or older. Race, minority status and gender will not affect enrollment.

**G. Human participants**

Twenty six participants of any gender/ethnic group, age 18 to 100 will be included.

***Inclusion Criteria:***

Male and female patients older than 18 year old

1. Patients who have been diagnosed with diastolic dysfunction by echocardiogram within 36 months of study enrollment, will be eligible for enrollment in the study.

***Exclusion Criteria:***

1. Left ventricular dysfunction (Left ventricular ejection fraction <40%)
2. Significant valvular disorder (i.e., prosthetic valve or hemodynamically relevant valvular diseases)
3. Recent (<6 months) stroke or myocardial infarction
4. Severe heart failure (NYHA class III or IV)
5. Recurrent vaso-vagal syncopal episodes
6. Unilateral or bilateral vagotomy
7. Pregnancy or breast feeding
8. Sick sinus syndrome (without a pacemaker), 2nd or 3rd degree AV block, bifascicular block or prolonged (PR>300ms) 1st degree AV block
9. Hypotension due to autonomic dysfunction

***2. Sources of research material:***

The research information will consist of echocardiographic parameters and HRV parameters.

***3. Plans for recruitment and consent procedures to be followed:***

***a. Location where consent is most likely to take place:***

Patients will be recruited from the outpatient clinics of the University of Oklahoma Health Sciences Center. The consent process will likely take place at the OUHSC Heart Rhythm Institute, 6th Floor Children's Hospital. All candidate subjects will have the purpose of the study explained to them, including benefits, risks and options. Subjects, will be asked to read the consent form. After all questions have been answered, they will be asked to participate. Finally, they will be asked to sign the consent form.

- b. Only English-speaking persons will be recruited. Non-English-speaking adults constitute less than 1% of the patients referred for ablation.

***c. Measures to decrease coercion of participants:***

Patients will have adequate time to review the consent. Recruiting of employees or staff by the principal investigator will be avoided.

**2. Risks and assess likelihood and seriousness:**

Transcutaneous VNS has generally been shown to be safe and well tolerated with only minor side effects, like tingling sensation, dysesthesia, skin redness and pressure marks at the site of stimulation, painful stimulation, dizziness, mild dyspnea and headaches. No significant effects on heart rate, blood pressure, or peripheral microcirculation could be detected during short term tVNS in a sample of 10 patients with tinnitus and in 22 healthy volunteers. In a pilot study of 24 patients with tinnitus treated with tVNS over 3-10 weeks, 2 adverse cardiac events (one classified as a severe adverse event) were registered but considered very unlikely to have been caused by tVNS since other explanations for the symptoms were evident. One patient had experienced sinus arrhythmic episodes already in the past, and in the other patient comorbid hypertension had caused concentric cardiac hypertrophy which might have contributed to the described temporary left bundle branch block. Retrospective analyses of ECG parameters revealed a trend toward shortening of the QRS complex by tVNS. This was observed after the 2 patients with cardiac adverse events were excluded from the analysis, but not when the whole sample of patients was analyzed. There was definitely no prolongation of the QRS complex which is a known predictor of cardiac morbidity and mortality. In conclusion, in subjects with no known pre-existing cardiac pathology, there has been no indication of arrhythmogenic effects of tVNS. This is in line with the low incidence of adverse cardiac reactions during the long-term experience in more than 50,000 patients with implanted left VNS for treatment of epilepsy and depression.

The risks of the study are considered minimal. The potential benefits in knowledge and determining whether there may be potential usefulness of this treatment therefore justify these risks. TENS is a noninvasive, well-tolerated modality that has been extensively used for treatment of pain in various settings. TENS has not been associated with side effects more than minimal discomfort at the area of application. Based on the FDA information sheet guidance for IRBs, clinical investigators, and sponsors, it is considered a non-significant risk device: <http://www.fda.gov/downloads/RegulatoryInformation/Guidances/UCM126418.pdf>. Previous studies examining TENS for vagus nerve stimulation in healthy individuals and in patients with tinnitus and epilepsy showed that this approach was safe and well tolerated. The ECG procedure for recording of HRV is similar to a routine ECG and is not associated with side effects or additional risks. The TENS unit used in this study has been deemed non-significant risk by the FDA.

**5. *Procedures for protecting against or minimizing potential risks:***

Risk should be no greater than minimal risk. The TENS unit used in this study has been deemed non-significant risk by the FDA.

**a. *Measures instituted to protect the privacy and/or confidentiality of participant PHI:***

The patient charts will be obtained after informed consent. A representative data sheet will be constructed and approved for confidentiality. Names will be replaced by numbers and the subject's code and name will be kept in separate repositories.

**6. *Potential benefits and importance to the participants and others:***

Heart failure with preserved ejection fraction (HFpEF) has become a major public health concern. Epidemiological studies have shown that the prevalence and hospitalizations related to HFpEF are increasing, and the growing elderly population is expected to further worsen these trends. Outcomes of patients with HFpEF are poor, and so far, no treatment has been shown to decrease morbidity or mortality. If this therapy proves to be effective in reversing diastolic dysfunction, a hallmark of HFpEF, both study participants and others may benefit from this non-invasive treatment option with less risk involved. The results of this study may provide the basis for the design of human studies using this modality to target selected populations with HFpEF.

**7. *Why risks are reasonable in relation to benefits:***

Heart failure with preserved ejection fraction (HFpEF) has become a major public health concern. Epidemiological studies have shown that the prevalence and hospitalizations related to HFpEF are increasing, and the growing elderly population is expected to further worsen these trends. Outcomes of patients with HFpEF are poor, and so far, no treatment has been shown to decrease morbidity or mortality. These proof-of-concept investigations will establish the first evidence of the effects of LLTS on LV diastolic dysfunction and may provide the basis for the design of further human studies using this modality to target selected populations with HFpEF. In light of the increasing number of patients with HFpEF and the poor success of the currently available treatment options, an alternative approach such as the one tested in this study, may benefit a large number of patients in Oklahoma.

**a. *Reporting mechanisms for adverse events to the IRB, FDA, and NIH:***

Clinical staff will track the following from patient report, physical assessments and documentation of clinical emergencies, adverse events according to federally published grading (0=no adverse event; 1=mild; 2=moderate; 3=severe and undesirable adverse events; 4=life threatening/disabling; or 5=death) and attribution (1=unrelated; 2=unlikely; 3=possible; 4=probable; 5=definite) scales. Clinical staff will report findings to the Investigator, who will then advise the IRB, NIH and FDA as indicated. Given the mild risk nature of the study, composite reports will be reviewed every ten patients to assure that untoward events do not occur systematically, and dropout cases will be reviewed singly to learn whether further inquiry or modifications should be made to improve study implementation.

**b. Adverse event (AE) grading**

0=no AE; 1=mild; 2=moderate; 3=severe and undesirable AE; 4=life threatening/disabling; or 5=death

